Aim 2: Quantify the magnitude of the effect of AEx + DDP intervention on UE impairment and function.

*Outcomes for Aim 2:* Two objective outcome measures, Fugl-Meyer Upper Extremity Assessment (FMA-UE) and Wolf Motor Function Test (WMFT), will be used to assess upper extremity impairment and function. This data will compared to historical controls from previous DDP trials from [name] (Co-I) lab.

Aim 3: Examine the relationship of biomarkers of neuroplasticity (BDNF and corticomotor excitability) and response to AEx + DDP.

*Outcomes for Aim 3:* We have selected transcranial magnetic stimulation (TMS)-based and blood-based measures to assess the neuroplastic potential of each subject as well as the acute effects of AEx+DDP on biomarkers of plasticity. These assessments will provide important data describing the neuroplastic potential of each subject (potential responders vs. non-responders) and the acute effect of AEx and DDP on indices of neuroplasticity.

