## 4.0 Inclusion and Exclusion Criteria/ Study Population

**Eligibility screening:** Subjects (male and female), ages 21-90, will be screened and recruited for the study six months to ten years post-stroke, allowing for natural recovery during the first 6 months post-stroke. The pool of candidates for the study will be recruited from the database registry supported by the Clinical and Translation Tools and Resources (CTTR) Core of the NIH-funded Center of Biomedical Research Excellence (COBRE) in Stroke Recovery at MUSC.. Eligible participants will be screened for participation and if appropriate will be accepted into the study.

**Inclusion criteria:** 1) experienced unilateral stroke at least 6 months, but no more than 120 months prior; 2) voluntary shoulder flexion of the affected arm  $\geq 20^\circ$  with simultaneous elbow extension  $\geq 10^\circ$ ; 3) moderate arm movement impairment (UE Fugl-Meyer Assessment  $> 21$  but  $< 52$  points; 4) passive range of motion in paretic shoulder, elbow, wrist, thumb and fingers within 20 degrees of normal; 5) 21-90 years of age; 6) ability to communicate as per the therapists' judgement at baseline testing; 7) ability to complete and pass an exercise tolerance test.

**Exclusion criteria:** 1) lesion in brainstem/cerebellum as these may interfere with visual-perceptual/cognitive skills needed for motor re-learning; 2) presence of other neurological disease that may impair motor learning skills; 3) orthopedic condition or impaired corrected vision that alters reaching ability (e.g., prior rotator cuff tear without full recovery); 4) paretic arm pain that interferes with reaching; 5) unable to understand or follow 3-step directions; 6) severe cognitive impairment (Montreal Cognitive Assessment score  $< 22$ ); 7) severe aphasia; 8) inability to read English, 9) history of congestive heart failure, unstable cardiac arrhythmias, hypertrophic cardiomyopathy, severe aortic stenosis, angina or dyspnea at rest or during ADL's; 10) Severe hypertension with systolic  $> 200$  mmHg and diastolic  $> 110$  mmHg at rest; 11) history of, or current, depression; **and for brain stimulation procedures only:** 12) women of child-bearing potential; 13) electronic or metallic implants; 14) history of seizures.

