### Screening and assessment visits

**Screening Assessments:** Following informed consent procedures we will perform screening assessments. Participants will be screened for cognitive function and depression with the Montreal Cognitive Assessment and Patient Health Questionnaire.

- **Montreal Cognitive Assessment (MoCA):** The MoCA is 30-point test used for assessing cognitive impairment. It assesses short-term memory recall, attention and concentration, executive function, language, visuoconstructional skills, orientation, and calculations. Subjects demonstrating cognitive impairment, indicated by a MoCA score < 22 will be excluded.
- **Patient Health Questionnaire (PHQ-9):** The PHQ-9 is a 9-item instrument used for screening and monitoring depression. Since depression has been shown to impact neuroplastic potential, subjects with depression (PHQ-9 > 4) will be excluded.
- **Transcranial Magentic Stimulation (TMS) Screen:** The TMS Screen has been developed from safety guidelines to ensure patients and study participants are safe to receive TMS. If the TMS screen identifies one or more contraindications to TMS subjects will be excluded from receiving TMS assessments.

**Clinical Assessments:** We will perform clinical assessments of UE impairment (FMA-UE), UE function (WMFT), and 'real world' arm use (SIS). This assessment battery is standard to most post-stroke rehabilitation trials. These data will help describe the functional status of participants. A licensed physical therapist, exercise physiologist, or trained study personnel through the South

Carolina Center for Stroke Recovery Research will perform all assessments. These assessments will be performed pre- and post-intervention (Pre Visit 1 and Post Visit 1).

- **Fugl Meyer Upper Extremity Assessment (FMA-UE):** The FMA-UE is a 33-item measure of UE impairment; however, the 3 items testing reflex response will not be administered because they do not measure a voluntary movement construct. Assessments will be video recorded and scored from the videos by trained, blinded raters. Each item will be scored on a 3-point rating scale (0=unable, 1=partial 2=near normal performance), item ratings will be summed and reported out of 60 points so that larger numbers indicate greater UE motor ability. The FMA-UE will be video recorded to allow for scoring by a blinded reviewer.

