## **11.0 Data Management**

**Power Analysis:** Although the primary goal of this proposal is to demonstrate feasibility and tolerability of AEx+DDP, the sample size is based on change in FMA-UE scores from recent work from Linder and colleagues. These data, for individuals with moderate UE impairment (the target sample of this study) yielded a FMA-UE mean change score of 12.3 for AEx + UE task practice and a FMA-UE mean change score of 4.4 for UE task practice only. Assuming the difference in mean FMA-UE change scores of 7.9 (pooled SD of 4.25), a sample size of n=5 for each group (AEx+DDP and DDP only) achieves 80% power with alpha = 0.05. Although we will not enroll a DDP-only group, we will be able to compare AEx+DDP to historical controls from the Co-I's lab. Two trials involving DDP have data from large samples (n=66 and n=103) providing ample data for comparison of AEx+DDP to DDP. Considering recruitment rates from the Co-I's previous trials (2-5 subjects/month) and anticipating a 20% dropout rate will inflate the sample size to n=10. Given recruitment rates and the timeline of this proposal (1 year) achieving this sample size appears feasible. This sample size is comparable to published literature and is sufficient to detect a large effect of AEx+DDP on FMA-UE compared to historical controls receiving DDP only. Additionally, this sample will provide a robust pilot data set for calculating effect sizes to power future trials examining AEx as primer for UE motor rehabilitation.

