**Statistical Analysis Plan:** Feasibility and tolerability metrics of adherence, retention, and acceptability will be assessed (Aim 1). FMA-UE, WMFT, and SIS data will be compared to historical control data from previous DDP trials from [name] lab (Aim 2). We will utilize ANOVAs to test the effect of adding AEx to DDP on the mean FMA-UE, WMFT, and SIS-hand item rating and the average SIS-recovery scores (PROC GLM, SAS v9.4). Additionally, data describing the effect of AEx+DDP on UE impairment and function will be used to generate effect sizes for future research proposals. Pre- and post intervention PAS assessment will be tested with a student's T-test or Wilcoxon rank-sum test based on distributional assessment. The acute (within session) and training (over the course of intervention) effect of AEx on BDNF and DDP on CME will be assessed with a generalized mixed model analysis (PROC MIXED). Relationships of biomarkers of plasticity (PAS, BDNF, CME) and response to AEx+DDP (change in FMA-UE or WMFT) will be explored with Pearson or Spearman-rank order correlational analysis, depending on distributional assessment (Aim 3).

**Confidentiality:** All records regarding participation in this study will be kept in locked file cabinets in the appropriate laboratories and/or offices, and stored on MUSC network storage. Access to linked identifiers is limited to research personnel intimately involved with the human subjects. All data and records acquired from subjects is for research purposes only and will be kept confidential and maintained in a secure database identifiable only by subject code. The results of the study may be published for scientific purposes; however, subjects' identities will not be revealed and data will not be traceable to any individuals in any resultant publications. The information gathered during this study will be kept confidential to the extent permitted by law.

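### Aim 2 compares AEx+DDP with non-randomised historical DDP cohorts by ANOVA, with no baseline adjustment and no control-selection rule, and reads the difference as the effect of adding AEx

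*Combined protocol and SAP*

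**What the plan says.** Section 1.0 (Outcomes for Aim 2) sets the comparison: "This data will compared to historical controls from previous DDP trials". Section 11.0 (Power Analysis) confirms that no DDP-only group is enrolled and names two earlier trials from the Co-I's lab, with n=66 and n=103, as the source of controls. The Statistical Analysis Plan in Section 11.0 then gives the test: "We will utilize ANOVAs to test the effect of adding AEx to DDP on the mean FMA-UE, WMFT, and SIS-hand item rating". SIS-recovery is included, and the procedure is PROC GLM.

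Three places bear on the scale of that test:

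- Power Analysis: "the sample size is based on change in FMA-UE scores from recent work", which points to change for FMA-UE.
- Statistical Analysis Plan, Aim 3: "response to AEx+DDP (change in FMA-UE or WMFT" is how response is defined there, again as change.
- Section 9.0, Clinical Assessments: "These assessments will be performed pre- and post-intervention (Pre Visit 1 and Post Visit 1", so each participant in this trial has one baseline and one post value.

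The Aim 2 sentence mentions neither change nor a covariate. For WMFT and SIS the power analysis gives no hint of the scale.

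Section 4.0 restricts this trial to FMA-UE above 21 and below 52, excludes MoCA below 22 and depression, and requires "ability to complete and pass an exercise tolerance test". No section says that the historical controls met any of these, whether the two trials are pooled, or whether their FMA-UE was scored on the 60-point version described in Section 9.0.

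**The concern.** Without randomisation, the contrast between cohorts contains any AEx effect plus every other difference between the people in them. Two such differences matter here.

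The first is baseline severity. On change scores, a gap in baseline severity cancels only if gain does not depend on baseline. On unadjusted post scores, most or all of it enters the estimate.

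The second is selection on other characteristics. Participants here must pass an exercise test and be free of depression. If the DDP-only controls were not so selected, any difference in gain that follows would be labelled an effect of AEx.

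Aim 2 holds the only comparison with DDP alone, and the sample size is justified by it. If the between-cohort estimate were passed to a later trial as an effect size, a cohort difference could mis-size that trial.

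**Working it through.** **Inputs from the documents.** Difference in FMA-UE change 7.9, SD 4.25, alpha 0.05 (taken as two-sided), n=5 per group, 10 enrolled with 20% dropout (so 8 to 10 analysed), controls 66 to 169 (66+103 if pooled), baseline FMA-UE 22 to 51.

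**Assumptions.** The documents give no historical baselines, no post-score SD and no relation of gain to baseline. Baseline SD is taken as uniform over the entry range, 29/√12 = 8.37. Baseline gaps of 3 and 5 points and slopes of 0, -0.2 and -0.3 (gain per baseline point) are illustrative.

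**The plan's own figure.** n = 2[SD(z0.975+z0.80)/δ]² = 2(4.25×2.80/7.9)² = 4.54, rounded up to 5. This reproduces. With the t distribution, 5 per group gives 73% power and 6 gives 83%. The comparison actually planned is much larger on the control side.

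**Power on change scores.** SE = 4.25√(1/8+1/66) = 1.59, and 7.9/1.59 = 4.97 on 72 df, giving 99.8% (noncentral t). Over 8-10 vs 66-169 it is 99.8% or more. If 4.25 is instead the residual SD around the baseline slope, the change SD rises to √(4.25²+(0.3×8.37)²) = 4.94 at slope -0.3, and the lowest power is 98.8%.

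**False positives with no AEx effect.** With baseline gap g and slope -b, the change-score contrast has mean b×g in absolute size (opposite in sign to the gap), and the post-score contrast has mean (1-b)×g. At g=5 the change-score bias is 0, 1.0 or 1.5 points and the post-score bias is 5.0, 4.0 or 3.5 points. Ranges cover 8-10 vs 66-169 and both readings of the 4.25 SD.

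| Slope | Change, 5-point gap | Change, 3-point gap | Post, 5-point gap | Post, 3-point gap |
|---|---|---|---|---|
| 0 | 5% | 5% | 29-37% | 13-16% |
| -0.2 | 9-11% | 6-7% | 27-35% | 13-16% |
| -0.3 | 13-19% | 8-10% | 25-35% | 12-16% |

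Example for change at slope -0.3, 8 vs 66: 1.5/1.59 = 0.94, rejection 15.3%.

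Adjusting the post score for baseline (ANCOVA, simulated, 20,000 runs) gives 4.6-5.4% across these slopes and gaps.

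**Selection that baseline does not capture.** Suppose the cohorts differ by an assumed 2 points in mean gain for reasons other than AEx. For 8 vs 66, 2/1.59 = 1.26, rejection 23.7%; for 10 vs 169, 2/1.38 = 1.45, rejection 30.1%. ANCOVA gives the same, 23.5-29.5% by simulation.

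**Limits of adjustment.** If the baseline is measured with reliability 0.9 (assumed) and a 5-point gap is stable, ANCOVA keeps a bias of (1-0.9)×5 = 0.5 points and rejects in 6-7%, while change scores stay near 5%. Neither method is free of bias for non-randomised groups.

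**The case against.** The strongest reply is that change scores are intended. The power analysis and the Aim 3 definition both point that way, and a group-by-time ANOVA on the two assessments would be the same test. This is the likelier reading for FMA-UE. A reader might infer instead that the plan analyses post scores, so that 25-37% false positives apply and the claim that the sample is "sufficient to detect a large effect of AEx+DDP on FMA-UE compared to historical controls receiving DDP only" fails. The documents do not support that: the claim sits inside a change-score calculation, where power is about 99%. What remains is that the Aim 2 sentence does not state the scale, that WMFT and SIS have no pointer in the power analysis, and that settling on change leaves control selection open.

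A reader might also infer that future trials will inherit a biased effect size. The plan says data on the effect of AEx+DDP "will be used to generate effect sizes for future research proposals". That may well mean a within-arm pre-post effect, which uses no historical controls. The risk applies only if a between-cohort estimate is used.

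The cohorts are not wholly undescribed: they come from the Co-I's lab, their sizes are given, and earlier DDP subjects averaged about 200 repetitions, the goal dose here. That is partial evidence of similar DDP exposure. It says nothing about baseline severity or eligibility.

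Finally, ANCOVA against change score is contestable for non-randomised groups. That stands, and it is why both should be reported.

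**Conclusion.** The point holds in a limited form. Aim 2 attributes to AEx a difference between non-randomised cohorts, with no baseline adjustment and no rule for who counts as a control. On the likelier change-score reading, power is not the problem (about 99%). False positives leave 5% only under assumptions: 9-19% for a 5-point baseline gap with gain falling 0.2-0.3 points per baseline point, and 6-10% for a 3-point gap. Selection is the larger exposure: an assumed 2-point difference in gain gives 24-30%, with or without adjustment.

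The gaps, slopes and baseline SD are assumptions, and the figures concern FMA-UE only. It would be too strong to say that the comparison is biased; the documents give neither baselines nor eligibility for the historical trials, so bias is possible but not shown. Feasibility and tolerability are primary, so this is a low-weight recommendation about a secondary aim.

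**What to change.** 1. **Controls.** Include only historical controls who meet this trial's FMA-UE range and any other of its eligibility criteria that those trials recorded, with FMA-UE on the same 60-point scale. State whether the two trials are pooled.
2. **Analysis.** State the scale for each measure. Replace the unadjusted ANOVA with a comparison adjusted for the baseline value of the same measure where the historical data hold it, and report the change-score comparison beside it.
3. **Wording.** Report the estimate with a 95% CI as the *difference from historical DDP*, not as the effect of adding AEx. Label any between-cohort effect size passed to future proposals in the same way. Within-arm effect sizes are unaffected.

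**Cost.** Some SAP wording, a little programming and fewer controls. At SD 4.25 with 8 participants, the 95% CI half-width, t×4.25√(1/8+1/m), is 3.03 points with m=169 controls and 3.17 with 66. Since 66 is one trial's whole sample, restriction could leave fewer: 3.43 with an assumed 30 controls and 3.65 with 20, a widening of 0.40 to 0.62 points over all 169. Baselines are already collected in this trial; whether the historical trials hold them for WMFT and both SIS items needs checking.

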## 5.0 Number of Subjects

A total of 10 chronic stroke survivors will be accrued locally.

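### The Aim 2 ANOVA sets 8–10 treated participants against much larger historical samples under one common variance, so its p-values and any interval are sensitive to unequal SDs

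*Combined protocol and SAP*

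**What the plan says.** Section 11.0, Statistical Analysis Plan, covers the Aim 2 comparison in one sentence: "We will utilize ANOVAs to test the effect of adding AEx to DDP on the mean FMA-UE, WMFT, and SIS-hand item rating", continuing with "the average SIS-recovery scores (PROC GLM, SAS v9.4". It states no variance check, unequal-variance test or robust standard error for these contrasts. The same paragraph does let distributional assessment decide the method for the PAS comparison and for the correlations.

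The group sizes come from three places:
- Section 5.0: "A total of 10 chronic stroke survivors will be accrued locally".
- Section 11.0, Power Analysis: "anticipating a 20% dropout rate will inflate the sample size to n=10", which implies about 8 completers.
- The same paragraph, on the controls: "Although we will not enroll a DDP-only group, we will be able to compare AEx+DDP to historical controls", and "Two trials involving DDP have data from large samples (n=66 and n=103) providing ample data for comparison of AEx+DDP to DDP".

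The plan does not say whether the two historical trials will be combined, kept apart, restricted or matched. The power calculation uses equal groups of 5 and a single pooled SD of 4.25 FMA-UE points. No SD is given for either group separately.

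**The concern.** An ordinary ANOVA F-test uses one error variance for all groups. With groups of similar size this does little harm even when the true variances differ. With 8–10 against 66 or more, the error variance is in effect the controls' variance, but the uncertainty in the difference is in effect the treated group's. The test then has its stated level only if the treated SD equals the historical SD.

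Nothing in the documents supports that equality. The controls come from other trials, and the treated group receives an added component whose effect may vary between people. If the treated SD is larger, p-values are too small and intervals too narrow. If it is smaller, the test is conservative and real differences are easier to miss.

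Aim 2 is secondary to feasibility. Its results are nevertheless meant to supply effect sizes for powering later trials, so the precision attached to the difference, and the SD in each group, will be carried forward.

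**Working it through.** **1. The plan's own figure.** Inputs from the Power Analysis: difference 7.9, pooled SD 4.25, alpha 0.05 (sidedness not stated), 80% power. Then d = 7.9/4.25 = 1.86. By the two-sided normal approximation, n per group = 2 × (1.96 + 0.84)² / 1.86² ≈ 4.5, which rounds up to 5. The stated 5 per group is reproduced. (The exact two-sided t-test has 73.1% power at 5 and 82.6% at 6.) This layout has equal groups and one SD. The planned analysis has a very different layout.

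**2. Where the variance and the sampling error come from.** With 10 treated and 169 controls (66 + 103):
- Controls' share of the error degrees of freedom: 168/177 = 95%. With 8 treated: 168/175 = 96%.
- Treated share of the sampling variance of the difference, at equal SDs: (1/10) / (1/10 + 1/169) = 0.1000/0.1059 = 94%.

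**3. One case in full.** Set the control SD to 1 and assume a treated SD of 1.5, with 10 against 169:
- Expected pooled variance = (9 × 2.25 + 168 × 1)/177 = 1.064
- SE used by the ANOVA = √[1.064 × (1/10 + 1/169)] = 0.336
- True SE = √(2.25/10 + 1/169) = 0.481
- Ratio = 0.70, so the ANOVA understates the standard error by 30%.

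At SD ratios 1.25 and 2 the corresponding figures are 0.82 and 0.55.

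**4. Type I error.** Simulation with normal data, equal means, a two-sided 5% test and at least 200,000 runs per setting. The SD ratio is an assumption throughout.

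| Treated vs control n | ratio 0.67 | 1.0 | 1.25 | 1.5 | 2.0 |
|---|---|---|---|---|---|
| 8 vs 66 | 0.8% | 5% | 9.9% | 15.2% | 24.1% |
| 8 vs 103 | 0.7% | 5% | 10.5% | 16.3% | 27.0% |
| 8 vs 169 | 0.5% | 5% | 10.9% | 17.5% | 28.9% |
| 10 vs 66 | 0.9% | 5% | 9.5% | 14.3% | 22.5% |
| 10 vs 103 | 0.7% | 5% | 10.4% | 15.8% | 25.6% |
| 10 vs 169 | 0.6% | 5% | 10.8% | 17.0% | 28.1% |

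The Welch (unequal-variance) test stays at 5.0–5.3% in every cell. For normal data, coverage of the pooled 95% interval is 100% minus the tabulated figure, whatever the true difference: for example 82.5–85.7% at ratio 1.5.

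**5. The imbalance is the cause.** With equal groups of 5, 8 or 10, the pooled test has a type I error of 5.2–5.9% at ratios 1.5–2.0.

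**6. A preliminary variance test would not protect the analysis.** Against 169 controls, an F-test detects a ratio of 1.5 only 47% of the time with 10 treated and 40% with 8.

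**The case against.** The strongest reply is that every rate away from 5% depends on an SD ratio that the documents do not give. That is right. At a ratio near 1.1 the damage is small (pooled coverage about 93%); it is moderate at 1.25 and serious only from about 1.4–1.5 upward. The direction is also open.

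A reader might infer that the plan itself expects the treated group to be more variable, because section 1.0 (Aim 3) speaks of the "neuroplastic potential of each subject (potential responders vs. non-responders", and might conclude that the Aim 2 results will be badly wrong. The documents do not support this. That sentence concerns neuroplastic potential and response to the combined intervention. It does not predict more spread than under DDP alone, and variation in response to DDP would be present in the controls too.

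Nor can the plan's figures be turned into a responder illustration. Suppose half the participants gain 4.4 points and half 20.2, each with SD 4.25. The treated SD is then √(4.25² + 7.9²) = 8.97. But 4.25 is already a pooled SD across an exercise and a non-exercise group, and equal groups with SDs 4.25 and 8.97 would pool to √[(18.06 + 80.47)/2] = 7.0. A 20.2-point gain is also impossible on the 60-point scale for anyone starting above 39.8, while entry allows scores up to just under 52.

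Three further replies stand in part:
- If exercise changes nobody's outcome and the groups are otherwise alike, the variances are equal and the p-value is valid. Inflated type I error needs effects that vary around a zero mean, or a variance difference from another source. Interval coverage suffers whenever the SDs differ.
- The plan does not commit to 169 controls. Using 66 or 103 changes little, but controls cut to about the size of the treated group would largely remove the problem.
- Feasibility is the primary goal, no decision rule rests on these p-values, and the plan promises effect sizes rather than intervals. The estimated mean difference itself is unaffected. This limits the weight of the point but not its validity.

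**Conclusion.** The point holds as one of sensitivity. An ordinary PROC GLM ANOVA of 8–10 treated participants against 66–169 historical controls has its stated error rate only if the two SDs are equal, and the plan neither supports that equality nor provides for its failure. Type I error at a nominal 5% runs from about 0.5–1% at a treated/control SD ratio of 0.67 to 22–29% at a ratio of 2, and is correct at 1.

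These figures assume normal data, an unadjusted two-group comparison, and controls kept at 66 or more. The SD ratio is an assumption and the direction of any departure is unknown. The documents do not show that the results will be wrong, only that the chosen method leaves them exposed when a cheap alternative would not. This merits a change to the SAP but is not a fundamental flaw.

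**What to change.** In section 11.0, Statistical Analysis Plan, prespecify an unequal-variance comparison for the AEx+DDP versus historical DDP contrasts on FMA-UE, WMFT and SIS. Use PROC MIXED with a REPEATED statement and GROUP= study group, with Satterthwaite or Kenward-Roger degrees of freedom. If the comparison is unadjusted, use the Satterthwaite t-test. Report the SD in each group and the difference with its 95% CI. Make this the planned analysis and do not let it depend on a preliminary variance test. State also which historical participants will be used and whether the two trials are combined.

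The cost is one SAP sentence and a line of code, plus some power if the variances are in fact equal. At d = 1.0 against 169 controls, power falls from 86% to 79% with 10 treated and from 78% to 67% with 8. At the plan's assumed effect (7.9/4.25 = 1.86) it stays at about 99%.

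The change does not address bias from comparing with non-randomised historical controls, which needs its own treatment.

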## Neurophysiological Assessments

- **Assessment of neuroplastic potential:** Participants' neuroplastic potential will be assessed with a plasticity-inducing paradigm called Paired Associative Stimulation (PAS). Briefly, PAS utilizes a repeated and timed peripheral nerve stimulation combined with transcranial magnetic stimulation (TMS) of the contralateral motor cortex to induce motor cortex plasticity. Prior to- and after PAS, corticomotor excitability (CME) is assessed via motor evoked potentials (MEP) which are obtained by single pulse TMS and electromyography (EMG) of a contralateral peripheral muscle. PAS will be assessed pre- and post-intervention (Pre Visit 3, Post Visit 2). PAS will be assessed in the ipsilesional motor cortex and paretic UE.
- **Paired Associative Stimulation:** Prior to PAS, all participants will be assessed for potential contraindications to TMS using a safety-screening questionnaire. First, we will use a combination of on-line surface electromyography (sEMG) recordings to view peak-to-peak motor evoked potential (MEP) amplitude and a neuro-navigation system to identify the optimal coil position for stimulation of the abductor pollicis brevis (APB) muscle (APB 'hotspot'). The area on the hand knob of the motor cortex that produces the largest and most consistent MEP's of the APB muscle will be marked as the 'hotspot' using the neuro- navigation system. We will then assess baseline cortical excitability by collecting a 'bin' of twenty test MEP's and a standardized stimulation intensity. This stimulation intensity will remain the same throughout the experimental session in order to allow for comparisons of MEP amplitude before and after PAS. After assessment of cortical excitability participants will receive PAS. For PAS, participants will receive a combination of simultaneous peripheral nerve stimulation and brain stimulation. Stimulation of the median nerve will be delivered via constant current stimulator (DS7A; Digitimer, Hertfordshire, UK) just proximal to the wrist. Bipolar electrodes will deliver a 200 $\mu$ s square wave pulse at an intensity equal to 300%

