sensory threshold. Single pulse TMS will be applied to the APB muscle representation on the contralateral motor cortex 25ms (ISI25) after the delivery of median nerve stimulation. A train/delay generator (DG2A; Digitimer, Hertfordshire, UK) will trigger paired peripheral nerve stimulation and brain stimulation. A total of 200 paired stimuli will be delivered at rate of .25 Hz, resulting in a total stimulation time of approximately 14 minutes. Bins of twenty test MEP's will then be collected immediately, fifteen, and thirty minutes post-PAS.

- **Electromyographic assessment:** Surface electromyography (sEMG) will be collected using 2cm by 2cm surface recording electrodes (Natus, Pleasanton, CA, USA) and will be placed perpendicular to the orientation of the fibers of the APB muscle belly. Prior to sEMG placement the site of the APB muscle will be lightly abraded and cleaned with pre-packaged alcohol swabs. All EMG signals will be collected using Spike2 v7.12 software (Cambridge Electronic Design; Cambridge, UK), amplified (x1000), bandpass-filtered (100-2000 Hz) using a CED 1902 amplifier (Cambridge Electronic Design; Cambridge, UK), and sampled at 5000 Hz using CED Micro 1401-3 data acquisition unit (Cambridge Electronic Design; Cambridge, UK). Data will be saved directly to a network drive for offline analysis. During all stimulation protocols sEMG activity will be continuously monitored in order to ensure that the APB muscle is not voluntarily active.
- **Assessment of DDP-induced CME:** The effect of DDP on CME will be assessed in the paretic UE. Before and after DDP on 3 occasions (DDP sessions 2, 10, and 17) a bin of twenty test MEP's will be collected. If reductions in impairments and improvements in function are mediated by a strengthening of the corticomotor pathway (eg. long-term potential-like response) we would expect DDP to increase CME. While PAS testing will provide information regarding the neuroplastic potential of each subject, this assessment will provide data describing the direct effect of a single and multiple sessions of DDP on the corticomotor pathway of the paretic UE.

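### The rank-sum test named for the pre/post PAS comparison is for independent samples, but PAS is measured twice in the same participants

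*Combined protocol and SAP*

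**What the plan says.** The Statistical Analysis Plan paragraph of section 11.0 states: "Pre- and post intervention PAS assessment will be tested with a" Student's "T-test or Wilcoxon rank-sum test based on distributional assessment". It does not say whether the t-test is paired, and neither a paired t-test nor a signed-rank test is named anywhere in the document.

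The schedule is under Neurophysiological Assessments: "PAS will be assessed pre- and post-intervention (Pre Visit 3, Post Visit 2". Both assessments use the ipsilesional motor cortex and the paretic arm.

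The Power Analysis paragraph of section 11.0 confirms that there is a single enrolled group: "Although we will not enroll a DDP-only group". Section 5.0 sets the total at 10. Outside controls are planned only for the clinical scales: "FMA-UE, WMFT, and SIS data will be compared to historical control data".

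For the acute and training effects on the other two biomarkers, BDNF and corticomotor excitability, the sentence after the PAS test says these "will be assessed with a generalized mixed model analysis (PROC MIXED").

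**The concern.** Two PAS results from one person are expected to be related. The rank-sum test takes its null distribution from two unrelated samples, so its reference distribution does not fit this comparison. If the distributional check selects the rank test and the analyst follows the text, the actual error rate depends on a pre/post correlation that the test ignores.

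Positive correlation makes the test conservative, so it can miss a real change in neuroplastic potential. Negative correlation makes it reject too often. The plan uses a model that can handle repeated measures for the other two biomarkers, and PAS is the exception.

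What is at stake is one mechanistic result under Aim 3. The Aim 1 feasibility outcomes, the Aim 2 comparisons and the planned Aim 3 correlations are not affected.

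**Working it through.** **Is there any second, independent PAS sample?**

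- Enrolled groups: one, of 10 people (sections 5.0 and 11.0).
- Historical controls: listed for FMA-UE, WMFT and SIS, not for PAS (section 11.0).
- PAS occasions: Pre Visit 3 and Post Visit 2, same hemisphere and limb (Neurophysiological Assessments).

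There is none. The two sets of values come from the same people and the contrast is paired.

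**Inputs for the size of the effect.** The plan gives no PAS figure to reproduce. From the documents: n = 10, and "anticipating a 20% dropout rate will inflate the sample size to n=10", so about 10 × (1 − 0.20) = 8 complete pairs. Assumed: bivariate normal pre and post values with equal SDs, pre/post correlation ρ, shift in units of that SD, exact two-sided tests at 0.05. The document states alpha 0.05 only for the FMA-UE calculation.

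**Why ρ matters.** With common SD σ, the variance of the difference between the post and pre means is

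Var = 2σ²(1 − ρ)/n,

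while an independent-samples test works with 2σ²/n. For the large-sample mean-based analogue, the actual two-sided error at nominal 0.05 is 2 × [1 − Φ(1.96/√(1 − ρ))]:

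- ρ = 0.5: 1.96/√0.5 = 2.77, giving about 0.6%.
- ρ = 0: 1.96, giving 5%.
- ρ = −0.3: 1.96/√1.3 = 1.72, giving about 8.6%.

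This shows the direction only. The small-sample rank tests were simulated with 100,000 replicates per cell.

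**Type I error of the rank-sum test on paired data**

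| ρ | 8 pairs | 10 pairs |
|---|---|---|
| −0.3 | 8.1% | 7.2% |
| 0 | 5.1% | 4.3% |
| 0.3 | 2.4% | 2.0% |
| 0.5 | 1.2% | 0.9% |
| 0.7 | 0.3% | 0.2% |

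The signed-rank test stays at 3.9–4.0% with 8 pairs and 4.8–5.0% with 10 pairs at every ρ. Its exact attainable levels are 3.91% and 4.88%. Those of the rank-sum test under independence are 4.99% and 4.33%. The small departures from 5% at ρ = 0 are therefore discreteness (plus simulation error), and the larger ones in the table are dependence.

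**Power for a 1 SD shift, rank-sum against signed-rank**

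| ρ | 8 pairs | 10 pairs |
|---|---|---|
| 0 | 44.0% vs 34.8% | 51.2% vs 49.7% |
| 0.3 | 43.7% vs 47.1% | 51.6% vs 64.2% |
| 0.5 | 43.8% vs 61.2% | 52.6% vs 78.5% |
| 0.7 | 44.5% vs 82.4% | 54.4% vs 94.2% |

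For smaller shifts at ρ = 0.5:

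- 0.8 SD: 26.6% vs 43.0% with 8 pairs, 32.3% vs 59.8% with 10.
- 0.5 SD: 9.1% vs 19.1% with 8 pairs, 10.3% vs 28.3% with 10.

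At 1 SD the signed-rank test overtakes at a ρ between 0.2 and 0.3 with 8 pairs, and between 0 and 0.1 with 10.

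**The t-test.** If it were run unpaired, the same fault would follow. In a run of 20,000 replicates with 10 pairs and ρ = 0.5, the unpaired t-test rejected a true null 0.95% of the time and the paired t-test 4.96%.

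**The case against.** The wording itself has no defence in the text, but there is a fair case that the matter is small.

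- **It is only a fallback.** The rank test is used only if the distributional check steers away from the t-test, and the PAS comparison is one mechanistic test in a feasibility pilot. Aim 3 as worded is about biomarkers and response, which the correlations address. This stands, and it limits the reach of the error.
- **Normal data are not the case in which the rank test would be chosen.** This stands in part. With lognormal values (log-scale SD 1, shift on the log scale, again assumed), power at 1 SD is 43% vs 43% with 8 pairs and ρ = 0.3, 43% vs 55% with 8 pairs and ρ = 0.5, and 52% vs 71% with 10 pairs and ρ = 0.5. The gain shrinks, but the type I error of the rank-sum test is unchanged, because the rank-sum test depends only on order.
- **There may be fewer than 8 pairs.** People with a TMS contraindication receive no TMS assessment. With 6 pairs, normal data and a 1 SD shift, power is 28% vs 26% at ρ = 0.3 and 27% vs 35% at ρ = 0.5. This also stands as a limit on the power gain.
- **Negative correlation is not suggested by anything in the documents.** This is true; conservatism is the likelier direction.
- **It may be a slip for the signed-rank test.** Quite possibly, but nothing in the document corrects it, and an analyst who followed the text would run the wrong test.

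None of these points makes an independent-samples test suitable for paired data.

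**Conclusion.** The concern holds. The rank-sum test is the wrong test for this comparison as written, and this follows from the design alone, without any assumed figure. The unspecified t-test is an ambiguity rather than an error.

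The size is uncertain because the plan gives no PAS correlation, SD or effect size. Under the normal-data assumptions above, a correlation of 0.5 cuts the actual type I error to about 1% and costs about 17 power points at a 1 SD shift with 8 pairs (61.2 − 43.8 = 17.4) and about 26 with 10 (78.5 − 52.6 = 25.9). Skewed data or fewer pairs reduce that loss. With 8 pairs and zero correlation the signed-rank test has about 9 points less power (44.0 − 34.8 = 9.2), partly because its attainable level is lower. The reason to change is that the test should match the paired design. A power gain is likely only if the correlation is clearly positive.

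The wording should be corrected before analysis, but it is confined to one Aim 3 test.

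**What to change.** Replace the PAS sentence in the Statistical Analysis Plan with wording such as: the within-participant change in PAS response (Post Visit 2 minus Pre Visit 3) will be tested with a paired t-test or a Wilcoxon signed-rank test, and reported with a 95% confidence interval and the number of complete pairs.

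A useful addition while that sentence is open: test responses "will then be collected immediately, fifteen, and thirty minutes post-PAS", so the plan should name in advance which of these times, or which average of them, defines the PAS response.

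The cost is one sentence of text. Visits, data collection and sample size do not change.
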